 - At screening (within 21 days prior to start of treatment (Visit 2) is accepted if compliant with central imaging requirements)
 - Every 6 weeks after Visit 2
 - Every 8 weeks after treatment week 24.

A 7-day interval before a scheduled tumour assessment is generally acceptable, except for the first imaging time point, which has to be at

least 6 weeks from randomization date. In the event of early discontinuation or an interruption/delay of study medication, the tumour imaging schedule should not be changed. After the database lock for primary analysis, the imaging intervals can change to follow local site standard (if no standard; every 16 weeks).

- 5) Only for patients permanently discontinuing study medication without disease progression: Follow imaging schedule every 6 weeks until PD or start of new anti-cancer therapy. After the database lock for primary analysis, the requirement to continue imaging will be removed.
- 6) During the treatment period, ECG will be assessed at Visit 4, 14, 26, and then every 16 weeks.
- 7) If not performed in the previous 8 days.
- 8) HRQOL: EORTC QLQ-C30, EORTC QLQ-H&N35, and EQ-5D, till the FUV. After database lock for primary analysis, collection of HRQOL will stop.
- 9) Treatment must commence as soon as possible after randomization, but within four days of randomization.

Proprietary confidential information. © 2019 Boehringer Ingelheim International GmbH or one or more of its affiliated companies

- 10) Continuous daily dosing, starting at Visit 2. For dosing, see [Section 4.1.3](#).
- 11) After one week of Afatinib treatment, treatment compliance should be discussed with the patient, to ensure that the medication is being taken correctly. When new medication is dispensed, treatment compliance is calculated and entered in the eCRF.
- 12) All adverse events, serious and non-serious, occurring from signing the informed consent onwards through the end of the follow up period will be collected, documented and reported to the sponsor by the investigator on the appropriate eCRFs/SAE reporting forms. Please refer to [section 5.2.2.2](#).
- 13) Only anti-cancer therapy will be collected in the observational period.
- 14) Includes haematology, serum biochemistry, and urinalysis. Urinalysis only at screening and EOT.
- 15) Only Visit 3 (i.e. not when Visit 3 is repeated as Visit 9, 15, and 21)

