The dose of Afatinib must be escalated to 50 mg (at the earliest after 28 days on study medication) if all the following criteria are met:

- CTCAE grade ≤ 1 skin rash (any aetiology/relation)
- Absence of diarrhoea, mucositis, and/or any drug-related event (any grade) other than skin rash CTCAE grade 1 and
- Compliance of Afatinib intake is in 80~100% as described in [Section 4.3](#)
- Dose was not previously reduced due to any of the AEs depicted in the dose reduction scheme (see [Table 4.1.4.1: 1](#))

Dose escalation is prohibited in any situation other than that described above. The patient should remain on 50 mg unless dose reduction becomes necessary (see Table 4.1.4.1: 1).

Dose reduction, Afatinib

Treatment related AEs will be managed by treatment interruptions and subsequent dose reductions of Afatinib according to the schedule described in Table 4.1.4.1: 1. Dose reductions

Proprietary confidential information. © 2019 Boehringer Ingelheim International GmbH or one or more of its affiliated companies

will apply to individual patients only. Once the dose has been reduced, it may not be increased later.

Table 4.1.4.1: 1 Afatinib dose reduction scheme

| AE type and CTCAE grade |
|--|
| Events related to study medication; 
• Any drug related AE grade ≥ 3.• Diarrhoea grade ≥ 2 persisting for 2 or more consecutive days (≥ 48 hours) despite adequate anti-diarrhoeal medication/hydration.• Nausea and/or vomiting grade ≥ 2 persisting for 3 or more consecutive days despite anti-emetic treatment/hydration.• Reduced renal function to grade ≥ 1 as measured by serum creatinine, proteinuria, or glomerular filtration rate. |
| Action |
| Interrupt Afatinib treatment until patient has recovered to grade ≤ 1 (note for reduced renal function, recovered to grade <1) or to the CTCAE grade present at baseline ¹ . If patient has not recovered within 14 days, study medication should be permanently discontinued ² . |
| Dose reduction scheme |
| Resume treatment at reduced dose according to; 
• 40 mg if the dose prior to the interruption was 50 mg.• 30 mg if the dose prior to the interruption was 40 mg.• 20 mg if the dose prior to the interruption was 30 mg. No dose reduction is allowed below 20 mg. |

1 Baseline is defined as the CTCAE grade prior to start of treatment

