5.2.3 Assessment of safety laboratory parameters

Blood and urine samples will be collected at the time points specified in the [Flow Chart](#) and analysed in a laboratory facility at (or close to) the investigational site. The sampling details are recorded in the eCRF. The laboratory report should be reviewed, signed and dated by the investigator.

Safety laboratory assessments may be performed according to local practice but must include at least the following parameters:

| | |
|--------------|--|
| Haematology | Red blood cell count (RBC), haemoglobin, haematocrit, white blood cell count (WBC) and differential, platelet count, reticulocyte number. |
| Biochemistry | Serum glucose, sodium, potassium, calcium (including ionized calcium), magnesium, creatinine, urea, aspartate amino transferase (AST), alanine amino transferase (ALT), alkaline phosphatase, lactate dehydrogenase, |

Proprietary confidential information. © 2019 Boehringer Ingelheim International GmbH or one or more of its affiliated companies

total bilirubin, γ -glutamyltransferase (GGT), albumin, creatine phosphokinase (CPK).

In case CPK is higher than ULN, further evaluation (e.g., by Troponin I assays, CPK isoenzymes and ECG exam) should be performed.

Glomerular Filtration Rate (GFR) will be estimated by the Cockcroft-Gault Formula utilising serum creatinine values (see [Appendix 2](#)).

Coagulation Prothrombin time (PT), partial thromboplastin time (PTT).

Urinalysis pH, glucose, erythrocytes, leukocytes, protein, nitrite will be analysed at baseline and EOT only. In case of values out of range, further evaluation should be performed.

Pregnancy test β -HCG testing in serum (alternatively in urine) will be performed in women of childbearing potential.

In case there is an obvious reason (for instance dehydration) for the laboratory results being abnormal at the screening visit, the laboratory sample(s) may be repeated.

The screening laboratory sampling must be done within two weeks before randomization. If the randomization is delayed beyond this, then the screening laboratory sampling must be repeated.

In case of neutropenia CTCAE grade 4, blood will be examined as clinically indicated at the discretion of the investigator until recovery.

Local lab results will be collected in the eCRF. Any AEs detected will be reported, see [Section 5.2.2.1.6](#).

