6.2.3 End of treatment and follow-up period

6.2.3.1 End of treatment visit

The end of treatment (EOT) visit will be performed when the patient permanently discontinues the study medication.

The decision to permanently discontinue study medication due to disease progression must be based on the evaluation of tumour imaging. If the decision to permanently discontinue the study medication is taken during a scheduled visit, the EOT visit procedures should be performed instead of the scheduled visit. If the decision is taken between scheduled visits, the EOT visit should be performed no later than seven days after the last treatment administration.

In the case study medication is permanently discontinued due to reasons other than disease progression or withdrawal of consent, the EOT visit will be performed, and the patient should continue the tumour imaging according to the pre-defined schedule until disease progression or start of other anti-cancer therapy. If a patient who did not have disease progression needs commence of other anti-cancer therapy, tumour imaging should be performed close to the start of new anti-other therapy. After the database lock for primary, the requirement to continue imaging for patients who permanently discontinued study medication due to other reasons than disease progression will be removed.

The investigator will, in consultation with the patient, decide the future treatment.

The patients that are still on treatment at one year after last patient randomized can continue drug administration from the trial, until disease progression or earlier if stop of treatment for other reasons is considered the best interest for the patient per investigator's judgment. An interim database lock will occur at around one year after last patient randomized. After this interim lock, only AE, dose change, drug termination date and cause of termination are required to be collected in RDC or BRAVE, and all the other trial procedures will be waived.

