7.3.3 Safety analyses

Safety analyses will be based on Treated Set, i.e., all patients who receive at least one dose of study medication will be included in the analysis of safety. The safety analysis will be descriptive and exploratory in nature. Adverse events will be graded according to United States NCI CTCAE, Version 3.0 ([R04-0474](#)).

Key safety measures will include:

- the overall incidence and intensity of AEs, as well as relatedness of AEs to treatment and seriousness of AEs
- AEs leading to dose reduction or permanent treatment discontinuation
- gastrointestinal events (vomiting, nausea, diarrhoea)
- skin reactions (rash, acne)
- other serious or significant AEs according to ICH E3
- decreased cardiac left ventricular function (reduction to below LLN and $\geq 20\%$ decrease compared to baseline)
- CTCAE grade 2 with increase by at least one CTCAE grade from baseline, for selected laboratory tests:
- (low values) haemoglobin, leukocytes (total WBC), neutrophils, lymphocytes, platelets, potassium
- (high values) PTT, creatinine, AST, ALT, bilirubin, alkaline phosphatase, proteinuria
- descriptive statistics for change from baseline for all laboratory tests
- causes of death.

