7.8.2 Laboratory data

The analyses of laboratory data will be descriptive in nature and will be based on BI standards [10]. Similar to AEs, lab values reported between drug start and 28 days after drug discontinuation will be analysed. CTCAE grades will be applied to applicable laboratory parameters according to NCI CTCAE v3.0.

Descriptive statistics of all laboratory values by visit will be provided including changes from baseline. Possible clinically significant abnormalities will be summarised by treatment group. For those lab parameters that have a CTCAE grading, possible clinically significant abnormalities are defined as post-baseline laboratory values with a CTCAE grade ≥ 2 that have had an increase of ≥ 1 grade from baseline. For those parameters for which no CTCAE grade has been defined, standard BI project definitions will be used to decide on clinical significance. Further frequency tables will show the transition of CTCAE grade from baseline to worst value and from baseline to last value on treatment.

The focus of the laboratory data analysis will be on the following laboratory parameters:

- Low values: haemoglobin, white blood cells, neutrophils, lymphocytes, platelets, potassium, sodium, GFR
- High values: creatinine, aspartate aminotransferase (AST), alanine aminotransferase (ALT), bilirubin, alkaline phosphatase

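### Proteinuria is a named trigger for afatinib interruption and a key safety measure, yet no urine test is scheduled between first dose and end of treatment

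*Protocol*

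**What the plan says.** **Dose rule.** Protocol 4.1.4.1, Table 4.1.4.1: 1, lists the drug-related events that call for afatinib to be interrupted and then resumed one dose step lower. One is reduced renal function of grade 1 or more, "as measured by serum creatinine, proteinuria, or glomerular filtration rate". The recovery condition carries its own renal clause: "note for reduced renal function, recovered to grade <1) or to the CTCAE grade present at baseline". Without recovery in 14 days, treatment stops permanently, unless sponsor and investigator agree otherwise for a patient with clear benefit.

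**Schedule.** The safety laboratory footnote, identical in the two flow charts, reads "Includes haematology, serum biochemistry, and urinalysis. Urinalysis only at screening and EOT". Section 5.2.3 places protein in the urinalysis panel and says that this panel "will be analysed at baseline and EOT only. In case of values out of range, further evaluation should be performed". On the timing of EOT, section 6.2.3.1 says: "The end of treatment (EOT) visit will be performed when the patient permanently discontinues the study medication".

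**Analysis.** Among the key safety measures, protocol 7.3.3 names the selected laboratory tests "high values) PTT, creatinine, AST, ALT, bilirubin, alkaline phosphatase, proteinuria". The corresponding focus list in SAP 7.8.2 reads "High values: creatinine, aspartate aminotransferase (AST), alanine aminotransferase (ALT), bilirubin, alkaline phosphatase". Proteinuria is not on it.

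**The concern.** A dose-modification rule can be applied evenly across sites only if the quantity it refers to is measured while a dose can still be changed. Here one of the three named renal measures has no scheduled value in that period. Whether proteinuria is found, and so whether the rule is applied to it, depends on whether a site happens to test urine outside the schedule.

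The same gap affects the safety analysis. A measure singled out as key would rest on a comparison of baseline with EOT. A low count could then reflect sparse testing as much as a low event rate, and the SAP's general rule for percentages does not separate the two.

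**Working it through.** The documents give no figure to reproduce. The check is a count of visits and a comparison of passages.

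**1. On-treatment safety laboratory visits to week 24.** Inputs: the flow chart for Visits 1 to 26 and its footnotes 14 and 15. Visit v falls at week v − 2, and Visits 3 to 8 repeat as 9 to 14, 15 to 20 and 21 to 26.

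- Visit 3 sample, first time only (footnote 15): Visit 3, week 1. That is 1 visit.
- Visit 5 sample and its repeats: Visits 5, 11, 17, 23, weeks 3, 9, 15, 21. That is 4 visits.
- Visit 8 sample and its repeats: Visits 8, 14, 20, 26, weeks 6, 12, 18, 24. That is 4 visits.

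Total: 1 + 4 + 4 = 9. In the second flow chart the samples fall at Visits 30 and 34 (weeks 28 and 32) and their repeats, that is, every 4 weeks.

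**2. How many include urinalysis.** By the footnotes of both flow charts and by section 5.2.3: 0 of the 9, and none of the later ones.

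**3. The three renal measures side by side.**

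| Measure in Table 4.1.4.1: 1 | Source | Scheduled values after first dose and before EOT, to week 24 |
|---|---|---|
| Serum creatinine | Blood biochemistry | up to 9 |
| GFR | Calculated from creatinine (5.2.3: "Glomerular Filtration Rate (GFR) will be estimated by the Cockcroft-Gault Formula utilising serum creatinine values") | up to 9 |
| Proteinuria | Urinalysis | 0 |

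Two of the three come from a single blood analyte. Proteinuria is the only one that is independent of creatinine, and it is the one without an on-treatment time point.

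**4. The rule, step by step, on scheduled proteinuria values alone.**

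- Trigger: the screening value precedes dosing, and the EOT value comes once treatment has stopped for good. Neither can prompt an interruption.
- Recovery: no scheduled value exists during an interruption, so return to grade below 1, or to the baseline grade, cannot be shown.
- The 14-day limit: it cannot be assessed for this component, for the same reason.

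**5. The safety summary.** SAP 7.8.2 analyses laboratory values from drug start to 28 days after discontinuation. The flow chart puts EOT 0 to 7 days after the last dose, so the EOT urinalysis falls inside the window. Scheduled post-baseline proteinuria values per patient: 1. An event that starts and resolves before EOT leaves no trace in scheduled data.

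**6. The denominator.** SAP section 7 takes percentages over all patients in the set, with or without a value, unless otherwise specified. Let N be the treated patients in an arm, n those with a post-baseline urine value, and x those with an abnormality. Then

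reported proportion = x/N = (x/n) × (n/N).

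If n is below N and x is above 0, the reported figure is below the proportion among those tested by the factor n/N. The documents do not give n/N, so the size of this effect is unknown.

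**The case against.** The table acts on drug-related adverse events from any source, not only on scheduled results. Visits are weekly, the 5.2.3 panel is a minimum, out-of-range urinalysis calls for further evaluation, and clinically relevant laboratory changes are recorded as adverse events. An unscheduled urine test can therefore set the rule in motion. Creatinine and calculated GFR are sampled throughout. All of this stands, and it limits the point to the proteinuria component and to scheduled data. It does not remove the contradiction, because nothing in the plan requires an on-treatment urine test in a patient whose baseline result was in range.

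A reader might infer more than the documents support:

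- *That afatinib continues at full dose in patients who meet the criterion.* Unscheduled testing, adverse event reporting and the other two renal measures can all lead to an interruption.
- *That all 220 planned afatinib patients are affected.* That is the size of the arm to which the rule applies. The documents give no rate of proteinuria, so the number affected cannot be stated.
- *That the safety measure is empty.* The EOT value allows a baseline-to-EOT comparison.
- *That the SAP drops proteinuria.* The focus list sets emphasis. SAP 7.8.2 also summarises all laboratory values by visit and tabulates abnormalities for parameters with a CTCAE grade, and SAP 7.8.1 plans tables for renal insufficiency.
- *That PTT has the same gap.* Section 5.2.3 puts coagulation in the minimum panel at the flow-chart time points with no restriction of its own. The flow-chart footnote does not mention it, which is at most an omission in a summary.

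**Conclusion.** The point holds in a limited form. Table 4.1.4.1: 1 and section 7.3.3 rely on proteinuria, while the flow charts and section 5.2.3 provide no urinalysis between first dose and EOT: 0 of 9 safety laboratory visits to week 24, and none of the 4-weekly visits afterwards. From scheduled data this component of the renal rule can be neither triggered nor shown to have resolved. The safety analysis has one scheduled post-baseline value per patient.

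This rests on reading the footnotes and section 5.2.3 as the complete urinalysis schedule; no other section adds a time point. The reading of the denominator assumes that the general rule in SAP section 7 applies to laboratory tables. The sponsor's laboratory display standard, which SAP 7.8.2 cites, is not part of the documents and might specify otherwise. The inconsistency bears on patient safety and is cheap to settle, so it should be settled.

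**What to change.** The sponsor should reconcile Table 4.1.4.1: 1 and section 7.3.3 with the urinalysis schedule in both flow charts and section 5.2.3, so that the renal rule, the key-measure list and the test schedule agree. Which clinical rule is right is not for a statistical review to say.

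If proteinuria remains a key measure, two changes follow in the SAP. Section 7.8.2 should name it in the high-value list. It should also be reported with the number of patients tested after baseline as denominator, in place of the default full set, and with that number shown. If the only scheduled post-baseline value is still the one at EOT, the table should say so, so that a low count is not taken as evidence of few events during treatment.

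Cost: wording changes in the protocol and a line or two in the SAP. Any cost of testing depends on how the sponsor resolves the conflict.

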2 In the event that the patient is deriving obvious clinical benefit in the opinion of the investigator, but has not recovered within 14 days, the further treatment with Afatinib will be decided in agreement between the sponsor and the investigator.

In the event of a treatment pause, subsequent visits should not be delayed.

In the event of a prolonged (≥ 7 consecutive days) CTCAE grade 2 drug-related event not listed in Table 4.1.4.1: 1, which is poorly tolerated by the patient, the investigator may interrupt the medication for up to 14 days to allow the patient to recover followed by a dose reduction according to the scheme in Table 4.1.4.1: 1.

Proprietary confidential information. © 2019 Boehringer Ingelheim International GmbH or one or more of its affiliated companies

In the event of any AEs other than listed in [Table 4.1.4.1: 1](#), the investigator may choose to interrupt the medication for up to 14 days to allow the patient to recover, but no dose reduction should occur.

If the investigator chooses to interrupt the study medication for more than 14 days but believes that the patient would derive clinical benefit from continuing medication, the decision to continue will be made by the sponsor in agreement with the investigator.

In case of major surgery, as judged by the investigator, it is recommended to interrupt Afatinib treatment around one week prior to the surgery, and to resume treatment after complete wound healing. If the medication is interrupted for more than 14 days, the decision to continue with Afatinib will be made by the sponsor in agreement with the investigator.

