4.2.3.1 Management of diarrhoea following treatment with Afatinib

Diarrhoea occurs at a high frequency and generally begins within two weeks of exposure to Afatinib. Although usually mild to moderate, diarrhoea may compel treatment modification or discontinuation, so early management is essential (see [Table 4.2.3.1: 1](#)). At the time of Afatinib initiation, patients should be given anti-diarrhoeal agents (such as loperamide). Investigator should ask patients to keep anti-diarrhoeal agents with them at all times, and instruct the

Proprietary confidential information. © 2019 Boehringer Ingelheim International GmbH or one or more of its affiliated companies

appropriate use. Patients should also be advised to drink adequate an amount of fluids during diarrhoea. For the use of anti-diarrhoeal medication, please refer to local SPC/PI.

Table 4.2.3.1: 1 Grade specific treatment of Afatinib related diarrhoea

| Severity (CTCAE grade) | Description | Intervention concerning Afatinib dose | Specific intervention |
|----------------------------|---|---|---|
| Mild (grade 1) | 
 Increase of <4 stools per day over baseline Mild increase in ostomy output compared with baseline | Continue same dose | 
 Stop laxatives and advise patient to drink sufficient water or clear fluids per day 4 mg (2 tablets) of loperamide to be taken immediately, followed by 2 mg (1 tablet) after each loose stool until bowel movements cease for 12 hours |
| Moderate (grade 2) | 
 Increase of 4-6 stools per day over baseline i.v. fluids indicated <24 hours Moderate increase in ostomy output compared with baseline; Not interfering with activity of daily life (ADL) | Continue same dose unless grade 2 diarrhoea continues for ≥2 days (48 hours) in which case treatment must be interrupted until recovered to grade ≤1 followed by dose reduction | 
 Continue loperamide Assess for dehydration and electrolyte imbalance Consider i.v. fluids and electrolyte replacement |

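### Protocol Section 4.1.4.1 gives conflicting instructions on reducing afatinib for a prolonged grade 2 event outside the reduction table, and on raising the dose again afterwards

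*Protocol*

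**What the plan says.** All the main text is in Protocol Section 4.1.4.1.

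**Unlisted events.** Table 4.1.4.1: 1 lists the triggers for reduction: any drug-related event of grade 3 or higher, persistent grade 2 or higher diarrhoea, persistent grade 2 or higher nausea or vomiting, and reduced renal function. Two consecutive paragraphs after the table deal with events it does not list.
- The first concerns a drug-related grade 2 event that lasts at least 7 consecutive days and is poorly tolerated. Here "the investigator may interrupt the medication for up to 14 days to allow the patient to recover followed by a dose reduction".
- The second concerns adverse events other than those in the table, without further limit. The investigator may pause treatment "to allow the patient to recover, but no dose reduction should occur".

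**Escalation.** The dose "must be escalated to 50 mg (at the earliest after 28 days on study medication) if all the following criteria are met". The criteria are rash no worse than grade 1; no diarrhoea, mucositis or other drug-related event; compliance of 80 to 100%; and, fourth, "Dose was not previously reduced due to any of the AEs depicted in the dose reduction scheme". The list is followed by "Dose escalation is prohibited in any situation other than that described above". The dose-reduction text then says: "Once the dose has been reduced, it may not be increased later".

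**Grade 2 diarrhoea of 48 hours.** Table 4.1.4.1: 1 requires persistence "despite adequate anti-diarrhoeal medication/hydration". The dose cell of Table 4.2.3.1: 1 has no such condition: treatment continues unless the diarrhoea lasts 48 hours, "in which case treatment must be interrupted until recovered to grade ≤1 followed by dose reduction".

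**The concern.** Two investigators who follow the section faithfully could treat the same patient differently. One may reduce for an unlisted grade 2 event where the other may not. After such a reduction, one would be obliged to go to 50 mg and the other forbidden to.

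The first question is not confined to rare events. Section 4.2.3 names dermatological events among the most common with afatinib. The rash and mucositis tables in Sections 4.2.3.2 and 4.2.3.3 have no dose column; both sections refer the reader to 4.1.4.1 for dose adjustment. Section 3.1 also stops treatment permanently when an event calling for a reduction still occurs at 20 mg, so whether an unlisted grade 2 event counts as one can bear on discontinuation.

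The second question concerns safety. The clause that makes escalation mandatory can apply to a patient whom another sentence protects from any increase, and its target is the dose that Section 4.1.3 identifies as the maximum tolerated dose.

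On the analysis side, SAP Table 6.2: 1, code C1, counts as an important violation a dose not paused and reduced as the protocol requires, or an escalation done improperly. One action can satisfy one sentence of the protocol and breach another, so sites and reviewers could code identical conduct differently.

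**Working it through.** No sample size, power or error rate is involved, and the plan states no figure to reproduce. The check traces example patients through the rules.

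**Trace 1: reduce or not.** A patient on 40 mg has drug-related grade 2 rash for 8 days, poorly tolerated.
1. Is the event in Table 4.1.4.1: 1? No. It is below grade 3 and is not diarrhoea, nausea or vomiting, or a renal event.
2. First paragraph: unlisted, grade 2, drug-related, at least 7 days, poorly tolerated. All conditions hold, so a pause and then a reduction is permitted.
3. Second paragraph: the event is not one listed in the table. The condition holds, so a pause is permitted but a reduction is not.

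Both paragraphs apply and their instructions differ. At stake is a step from 40 to 30 mg: 30/40 = 0.75, a 25% cut that the section describes as permanent.

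**Trace 2: barred from 50 mg or required to take it.** The same patient was reduced to 30 mg under the first paragraph. The rash is now grade 1 or less, and more than 28 days on study medication have passed.

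| Escalation criterion | Met? |
|---|---|
| Rash no worse than grade 1 | Yes |
| No diarrhoea, mucositis or other drug-related event | Yes (assumed) |
| Compliance 80 to 100% | Yes (assumed) |
| No earlier reduction for an event in the table | Yes, because the event was by definition unlisted |

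All four are met, so escalation to 50 mg is required. The dose-reduction text bars any increase after a reduction, whatever its cause. The clause prohibiting escalation in other situations does not settle this, since the patient is in the situation described. Nor does the current dose: the afatinib list does not mention it, whereas Table 4.1.4.2: 1 for methotrexate limits its escalation column to one current dose.

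Size of the step after one unlisted-event reduction:
- from 30 mg: 50/30 = 1.67, or +67%;
- from 40 mg, for a patient reduced from 50 mg: 50/40 = 1.25, or +25%.

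**Trace 3: grade 2 diarrhoea for 48 hours.**
- With adequate anti-diarrhoeal treatment and hydration, both tables say interrupt, recover to grade 1 or less, then reduce. They agree.
- Without it, the management table says interrupt and reduce, while the condition in the reduction table is not met. The tables differ only here.

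**The case against.** The best defence on unlisted events is to read the second paragraph as covering whatever the first leaves over. The first is narrow and discretionary, the two are adjacent, and a literal reading of the second leaves the first with nothing to do. That is a sensible reading and may be the intended one, but no wording says so. The corresponding methotrexate paragraph in Section 4.1.4.2 does limit its scope, to unrelated events.

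On re-escalation, the defence is that the bar on later increases is explicit, unconditional and in the same section, and that Sections 2.3, 3.1 and 4.1.3 present escalation as being for patients with no or minimal adverse events. The case also arises only after a discretionary reduction for an unlisted event; if the second paragraph governs, it never arises that way. All of this narrows the problem. It does not remove it, because the escalation clause is mandatory and its fourth criterion is narrower than the bar. Moreover, the residual reading that rescues the first point makes reductions for unlisted events legitimate, and so brings the second conflict into play.

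On diarrhoea the defence largely succeeds. Threshold, duration and action agree. Table 4.2.3.1: 1 starts loperamide at grade 1 and continues it at grade 2. Section 4.2.3.1 has patients supplied with anti-diarrhoeals from initiation, and Section 4.2.3 sends dose modifications to 4.1.4.1. A reader might infer a third contradiction of equal weight; the documents support only a mismatch in wording.

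A reader might also infer damage to the efficacy results. Protocol Section 7.3.1 and SAP Section 6.3 analyse efficacy as randomised, and SAP Section 6.2 plans no per-protocol analysis, so code C1 removes nobody. C1 is also not among the violations identified by program. The dose-level and time-to-first-reduction summaries in SAP Section 7.7 can be computed from doses actually given, although ambiguous rules may affect what those doses were.

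**Conclusion.** The concern holds for two linked contradictions in Section 4.1.4.1: whether a prolonged, poorly tolerated, unlisted grade 2 drug-related event may lead to a reduction, and whether a patient so reduced must later go to 50 mg or may not be increased at all. The diarrhoea wording is a minor third item, relevant only to a patient without adequate anti-diarrhoeal treatment.

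The first point decides a 25% reduction from 40 mg. The second decides an increase of 67% from 30 mg, assuming that the event resolves, no other drug-related event remains and compliance is in range. The number of patients affected cannot be derived from the documents.

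Two larger figures should not be attached to this point. A step from 20 to 50 mg (50/20 = 2.5, or +150%) needs two successive reductions, both for unlisted events, because any reduction for a listed event triggers the fourth criterion. The grade 3 diarrhoea and rash rates in Section 4.1.3 (24% and 25% against 7% and 7%) compare starting doses in lung cancer patients. They illustrate dose sensitivity and do not estimate the risk of re-escalation in this trial.

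The consequences are for patient safety, uniform dosing across sites and consistent coding under C1. The primary analysis is not affected.

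**What to change.** Reconcile the following texts. Which rule stands is for the sponsor's clinicians, and nothing here favours one.

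1. In Section 4.1.4.1, word the two consecutive paragraphs on unlisted events so that no event falls under both.
2. In the same section, make the fourth escalation criterion and the bar on later increases agree, and state the current dose to which the escalation rule applies.
3. Use the same trigger wording for 48-hour grade 2 diarrhoea in Tables 4.1.4.1: 1 and 4.2.3.1: 1.
4. Apply SAP code C1 against the reconciled text. SAP Section 6.2 treats the violation list as a working list to be finalised before the primary analysis.

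The cost is a few sentences in Section 4.1.4.1 and one table cell in Section 4.2.3.1. No visit, procedure or analysis is added.
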